## 11.3 OVERVIEW

In addition to reporting the observed fraction with toxicity, the 80% and 95% confidence intervals about this fraction will be reported.

At the conclusion of the study, the overall fractions with cardiac toxicity among 18, 24 or 30 patients enrolled at one dose or within the entire cohort will be determined. For illustrative purposes only, under a simplifying assumption that the 18-30 patients were enrolled in a single cohort without any intermediate evaluations, the following probabilities suggest that 2+/18, 2+/24 or 3+/18 with cardiac toxicity are more likely to be associated with 15% toxicity (arbitrarily chosen to substantially exceed 7%) than with 3% (arbitrarily chosen to be well below 7%).

In any given 18 patients assessed for toxicity, if two or more of the 18 develop toxicity:

- There is a 10% probability of this occurring if the true toxicity is 3%.
- There is a 78% probability of this occurring if the true toxicity is 15% (potentially unacceptable).

In any given 24 patients assessed for toxicity (6 at one dose level and 18 at a second level), if two or more of the 24 develop toxicity:

- There is a 16% probability of this occurring if the true toxicity is 3%.

- There is an 89% probability of this occurring if the true toxicity is 15% (potentially unacceptable).

If there are 30 patients assessed for toxicity (18 at one dose level plus 6 at one level and 6 at another level), if three or more of the 30 develop toxicity:

- There is a 6% probability of this occurring if the true toxicity is 3%.
- There is an 85% probability of this occurring if the true toxicity is 15% (potentially unacceptable).

As of 12/11/15, 0 of 20 patients enrolled to date that have received a minimum of 2 doses of AdHER2 DC vaccine have developed cardiac toxicity. Since we have observed 0 of 20 subjects with cardiac toxicity, this would have a 68% chance of occurring if the true probability of cardiac toxicity for a given patients was 2%; similarly, it would be 36% if the probability of cardiac toxicity was 5%, 12.2% if the probability of cardiac toxicity was 10% and 3.8% if the probability of cardiac toxicity was 15%. We are assuming that the probability of cardiac toxicity is no more than 10% since higher probabilities of toxicity are associated with a much lower chance of seeing 0 of 20 patients with cardiac toxicity as has been observed.

Since 0 of 20 patients already have been documented to have NO cardiac toxicity, and 0 to 2 patients out of 30 would have been acceptable per the original study design, a statistical estimate was performed to determine what the probability of having 0 to 2 of the next 10 patients in the Part 1 Expansion Cohort having cardiac toxicity would be. If the probability of cardiac toxicity were 2%, there would be 99.91% probability of 0 to 2 of 10 with toxicity; if it were 5%, there would be 98.8% probability; and if it were 10%, there would be 93% probability of 0 to 2 of 10 with toxicity. Thus, assuming the next 10 patients would have the same underlying per-patient probability of developing cardiac toxicity as the first 20 had, and it is likely to truly be at or below 10%, there is between a 93% and 99.9% probability that the next 10 patients enrolled in the Part I Expansion Cohort would have 0 – 2 toxicities and therefore 0 – 2 of 30 would have cardiac toxicity as per the original study design. Consequently, FDA approval was received on 12/14/15 to initiate enrollment in Part II of the study in parallel, while enrollment of the Part I Expansion Cohort is completed.

The fraction of subjects with immunogenicity, defined as a 3-fold increase in anti-HER2/neu antibody concentration (measured as mcg/mL) or a 4-fold increase in antibody dilution titers over baseline will be reported, along with 80% and 95% confidence intervals, at the following time points: Weeks 4 (after 1 vaccine dose), 8 (after 2 vaccine doses), 12 (after 3 vaccine doses), 28 (after 5 vaccine doses), 48 and 52 weeks and during extended follow-up for monitoring of cardiac adverse events at weeks 76, 100 and 124.

Finally, as a secondary objective, the fraction of subjects who have stable disease, an objective partial response or better by modified irRC will be determined along with appropriate confidence intervals with exceptions to the PR assessment at Week 12 as noted in Sections [3.5.1](#), [3.5.2](#) and [6.2.4](#). The fraction identified in this trial will potentially be useful information for design of any subsequent trials using this vaccine in both of the patient populations being studied.

Part I of the study will accrue both males and females with HER2 expressing metastatic cancers for whom trastuzumab is not indicated and who are naïve to HER2-directed therapies. Accrual to Part II of the study will be restricted to females or males with recurrent or progressive metastatic breast, gastric/gastroesophageal or other cancers that have received clinically

indicated prior treatment with trastuzumab, pertuzumab, lapatinib, ado-trastuzumab emtansine or other HER2-directed therapies. The study will seek to accrue racially and ethnically diverse population affected by the cancer types targeted for enrollment in this study.

We expect to accrue at least 2 patients per month with expected completion of accrual within 2.5 years. If after 2 years, 20 or fewer patients have been accrued to Part I of the study, the study will be terminated for failure to accrue at a viable rate. If accrual to Part I of the study has been completed and enrollment in Part II has begun, if after 1 year, 10 or fewer patients have been accrued to Part II of the study, the study will be terminated for failure to accrue at a viable rate. To allow for the possibility of invaluable patients, an accrual ceiling of 65 will be used.

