#### Arms

Number	Name	Description
1	Part I dose escalation	AdHER DC vaccine administered at escalating doses.
2	Part I dose expansion	AdHER DC vaccine administered at $40 \times 10^6$ dendric cells maximum.
3	Part II dose escalation	AdHER DC vaccine administered at Dose Level 1.
4	Part II dose expansion	AdHER DC vaccine administered at $40 \times 10^6$ dendric cells maximum.

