### Proposed Dosage and Administration

This part of the study will enroll patients in the vaccine dose levels outlined below:

Dose Level 1 (N = 6 patients):	$5 \times 10^6$ viable cells/vaccine
Dose Level 2 (N = 6 patients):	$10 \times 10^6$ viable cells/vaccine
Dose Level 3 (N = 6 patients):	$20 \times 10^6$ viable cells/vaccine
Expansion Cohort (N = 12 patients):	$40 \times 10^6$ viable cells/vaccine

Autologous AdHER2 DC vaccine will be administered intradermally at Weeks 0, 4, 8, 16 and 24. Response will be measured as outlined in section [6.2](#). Vaccine dose escalation will follow the procedures specified in Section [3.1.2](#).

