### **Proposed Dosage and Administration**

Part II of the study will enroll 30 breast, gastric/gastroesophageal or other cancer patients as outlined in the vaccine dose cohorts outlined below:

Dose Level 1 (N = 6 patients):  $20 \times 10^6$  *viable* cells/vaccine

Expansion Cohort (N = 24 patients):  $40 \times 10^6$  *viable* cells/vaccine

Autologous AdHER2 DC vaccine will be administered intradermally at Weeks 0, 4, 8, 16 and 24. Re-staging will be performed as outlined in Section **6.2**. Vaccine dose escalation will follow the revised procedures specified in Section **3.1.2**.

Abbreviated Title: AdHER2/neu DC Vaccine

Version Date: 07/22/2019

Figure 11: AdHER2 Autologous DC Vaccine Study Schema

	Screen Consent Baseline	Week 0	Week 4	Week 8	Week 12	Week 16	Week 20	Week 24	Week 28	Week 32	Week 36	Week 40	Week 48	Week 60	Week 76	Week 100	Week 124
Vaccine		V	V	V	V	V	V										
Echo	V		V	V	V	V	V	V	V	V	V	V	V	V	V	V	V
Scans	V			V	V	V	V	V	V	V	V	V	V	V	V	V	V
Correlatives	V			V	V	V	V	V	V	V	V	V	V	V	V	V	V

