#### **7.5.2 Safety Monitoring Committee (SMC)**

This protocol will require oversight from the Safety Monitoring Committee (SMC). Initial review will occur as soon as possible after the annual NIH Intramural IRB continuing review date. Subsequently, each protocol will be reviewed as close to annually as the quarterly meeting schedule permits or more frequently as may be required by the SMC. For initial and subsequent reviews, protocols will not be reviewed if there is no accrual within the review period. Written outcome letters will be generated in response to the monitoring activities and submitted to the Principal investigator and Clinical Director or Deputy Clinical Director, CCR, NCI.

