*Dose escalation will proceed as long as 0 of 6 or 1 of 6 patients within a dose level have no evidence of toxicity and at least 3 of the 6 patients within a level have reached Week 12 on study. If 2 of 6 patients on any given dose level develop cardiac toxicity, that dose cohort will be closed to further accrual, no higher doses will be explored, and dose expansion of an additional 12 patients will be enrolled in the next lower dose level to further assess for cardiac toxicity. The vaccine dose at which 0 to 1 of 18 treated patients in Dose Levels 1 to 3 develop cardiac toxicity will be defined as the maximum tolerated dose (MTD). If two or more patients out of 18 at a given dose have developed cardiac toxicity, then the MTD will have been exceeded at that dose, and the dose level below that one will be considered the MTD. Since enrollment in Dose Level 3 has been reached and 0 of 6 patients has toxicity, then an expansion cohort of an additional 12 patients will be added, for a maximum targeted accrual of 30 patients in Part 1. The Expansion Cohort will be treated at  $40 \times 10^6$  viable cells/vaccine and will be monitored for toxicity in an identical manner as previously identified. The 12 patients will be accrued at the  $40 \times 10^6$  level without any planned interim stop, as cardiac toxicity is not presently anticipated given the results as of 12/11/15. With all 12 enrolled as a single cohort, there is a 4.9% probability of having 2 or more of 12 patients with cardiac toxicity if the true probability for a given patient is 3%, and 55.7% of having 2 or more of 12 with cardiac toxicity if the true probability for a given patient is 15%. Therefore, observing 0-1 of 12 with toxicity would be acceptable, and  $40 \times 10^6$  would be considered the maximum evaluated and tolerated dose. If we observe 2 or more with cardiac toxicity at or before accruing the 12th patient, this exceeds a safe level. Further patients would be added subsequently, by amendment, to the next lower dose, to confirm its safety.*

***To ensure that the trial does not continue to accrue patients in the event that a much greater incidence of toxicity than expected would be recognized early, the following early stopping rules for accrual will be invoked in each part of the study if:***

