## 11.2 PART II (MAXIMUM OF 30 EVALUABLE PATIENTS)

Since the risk for cardiac toxicity may differ in individuals who have previously received HER2-directed therapy, the FDA is requesting that repeat dose escalation of AdHER2 DC vaccination be conducted in Part II of the study *in a population with prior exposure to trastuzumab, pertuzumab, lapatinib, ado-trastuzumab emtansine (TDM1) and other HER2-directed therapies.* This population will include adults with recurrent or progressive, metastatic breast, gastric/gastroesophageal or other cancers with 1+ to 3+ HER2/neu expression by IHC or an equivocal or positive FISH result. Vaccine dose escalation will be repeated to again determine whether there is an adverse safety signal regarding cardiac toxicity, in addition to assessment of the vaccine's immunogenicity and clinical activity. Vaccine dose escalation, administration, re-staging assessment and early stopping rules that will be invoked that are identical to that conducted in Part I.

The goal is to accrue up to 30 evaluable patients in Part II of the study and treat them with the experimental AdHER2 vaccine.

Unless an early stopping rule is invoked in either Part I or Part II of the study, the number of patients who have experienced a clinically significant cardiac toxicity will be determined to estimate the frequency of cardiac toxicity. In addition, the dose level(s) at which toxicity is observed will also be examined.

*If in part I, dose escalations have taken place in the first three dose levels and 0 of 20 patients have experienced cardiac toxicity, Part II of the study in patients with metastatic breast cancer and prior exposure to HER2-directed therapies will proceed with vaccine dosing based on the safety confirmed in Part I and as outlined in Section 3.1.2.* A maximum accrual of 30 patients will be enrolled in Part II and patients will continue to enroll on that dose unless 3 patients have experienced cardiac toxicity.

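### Both parts treat at 40 x 10^6 in parallel, but the cardiac limits disagree and no rule says what a breach in one part means for accrual at that dose in the other

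*Combined protocol and SAP*

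**What the plan says.** **Dose and timing.** The dosage tables in Section 3.1 and the arm list in Section 2.4.1 assign 40 x 10^6 cells to both expansion cohorts, 12 patients in Part I and 24 in Part II. Part II first treats 6 patients at 20 x 10^6. Section 11.3 reports approval "to initiate enrollment in Part II of the study in parallel, while enrollment of the Part I Expansion Cohort is completed".

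**Part I limit.** Sections 3.1.2 and 11.1 say that "observing 0-1 of 12 with toxicity would be acceptable". The opposite case begins "If we observe 2 or more with cardiac toxicity at or before accruing" the 12th patient. It is classed as above a safe level, and further patients are then to be added by amendment at the next lower dose.

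**Part II limit.** Section 11.2 makes two statements. One is that the Part II early stopping rules are the same as in Part I. The other is that "patients will continue to enroll on that dose unless 3 patients have experienced cardiac toxicity". It does not name the dose meant or the number of patients over which the 3 are counted.

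**Limit behind the parallel start.** Section 11.3 takes 0 to 2 events in 30 as acceptable under the original design. With 0 of 20 observed, it treats 0 to 2 events among the next 10 Part I expansion patients as acceptable.

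**Other safeguards.**
- The 2-of-6 rule and the vaccine-related death rule (Sections 3.1.1 and 11.1) are invoked within each part.
- The study-wide cardiac rule (Section 11.4) counts only the first 10 and the first 20 patients enrolled.
- For the Safety Monitoring Committee, Section 7.5.2 says "each protocol will be reviewed as close to annually as the quarterly meeting schedule permits", or more often if the committee requires.
- Under Section 7.5.1 the research team reviews each patient weekly while patients are on active treatment.

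**The concern.** Two cohorts receive the same dose of the same product over overlapping calendar time, and each is judged only against its own count. If Part I reaches its limit at 40 x 10^6, the plan calls the dose unsafe in one section, while another section, followed literally, keeps enrolling patients on it. No section says what the Part I finding does to Part II, or the reverse.

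The three statements of the limit also disagree. Section 11.2 conflicts with itself. The tolerance used in Section 11.3 to open Part II early is looser than the limit in Section 11.1 for the same Part I patients.

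This matters more here than for an ordinary drug. The protocol says that the induced immune response cannot simply be switched off (Sections 3.3 and 12.5), that cardiac risk may differ in previously treated patients (Section 11.2), and that stringent stopping rules cover late as well as early cardiac signals (Section 12.5). Echocardiograms run to Week 124, so a Part I breach can emerge after its cohort has filled.

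**Working it through.** **1. Reproduce the plan's figures.** With X the number of events in the 12 Part I expansion patients, P(X ≥ 2) = 1 − (1−p)^12 − 12p(1−p)^11. This gives 4.9% at p = 3% and 55.7% at p = 15%, as in Section 11.1. For 0 to 2 events in 10, the binomial gives 99.91%, 98.8% and 93.0% at 2%, 5% and 10%, as in Section 11.3.

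**2. Compare the Section 11.3 tolerance with the Section 11.1 limit.** The 10 patients in Section 11.3 belong to the 12-patient expansion cohort. Two events among them already make at least 2 of 12, which Section 11.1 calls above a safe level. The probability consistent with Section 11.1 is therefore at most that of 0 or 1 event in 10:

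| True rate | P(0–2 of 10), as in 11.3 | P(0–1 of 10) |
|---|---|---|
| 2% | 99.9% | 98.4% |
| 5% | 98.8% | 91.4% |
| 10% | 93.0% | 73.6% |

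At 10%, the ceiling that Section 11.3 itself assumes, the reassurance falls from 93.0% to 73.6%.

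**3. Chance that the two parts end with discordant counts.** Let Y be the number of Part II events. Assume independent parts and the same true rate p in both. Discordance = P(X ≥ 2 of 12) × P(Y ≤ 2 of n). Section 11.2 gives no n, so two values are shown: n = 24 (the Part II expansion cohort) and n = 30 (all of Part II, with the same rate assumed at both of its doses).

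| p | P(X ≥ 2 of 12) | P(Y ≤ 2 of 24) | Discordance, n = 24 | P(Y ≤ 2 of 30) | Discordance, n = 30 |
|---|---|---|---|---|---|
| 3% | 4.9% | 96.6% | 4.7% | 94.0% | 4.6% |
| 7% | 20.3% | 76.6% | 15.6% | 64.9% | 13.2% |
| 10% | 34.1% | 56.4% | 19.2% | 41.1% | 14.0% |
| 15% | 55.7% | 28.0% | 15.6% | 15.1% | 8.4% |

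**4. Add the 2-of-6 rule.** Suppose Part II must also have no more than 1 event in its first 6 patients at 40 x 10^6. The n = 24 figures become 4.7%, 15.3%, 18.7% and 15.1%, a reduction of under 1 percentage point in each case.

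**5. What these figures measure.** They compare final counts and ignore timing. They include Part I breaches that arise after Part II has filled. They are therefore upper bounds on the chance that Part II is still accruing at a Part I breach and then runs to full accrual without meeting its own limit. They leave out cases where Part II enrolls for a time after a Part I breach and later stops on its own count. The chance of any Part II enrollment after a breach is bounded only by the breach probability in the second column.

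**6. Look for a link elsewhere.** The Section 11.4 rule cannot count patients after the 20th. The wording in Sections 3.1.2 and 11.2 that bases Part II dosing on Part I safety is an entry condition (0 of 20), already met on 12/11/15. Neither the committee nor the weekly team review is given a trigger tied to a cardiac finding in the other part.

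**The case against.** The strongest reply is that oversight is not absent. The committee may meet more often than yearly, the team reviews patients weekly, serious events go to the sponsor within 24 hours, and the investigator can end the study. A Part I breach also leads to an amendment before patients are added at the next lower dose, which is a natural moment to consider Part II. All of this stands, and it makes continued enrollment after a breach less likely in practice. None of it is a pre-specified response in Part II to a finding in Part I.

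Several stronger readings are tempting, but the documents do not support them.

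- *The two parts definitely have different limits.* Section 11.2 also says the rules match Part I, and the 2-of-6 rule applies in each part. What is established is a contradiction. Matching limits applied per part would still lack a link.
- *About 19% is the chance that Part II keeps enrolling on a dose found unsafe.* It is the chance of discordant final counts, at one assumed rate and one assumed denominator.
- *Part II continues on a premise that can later fail.* The reference to Part I safety is an entry condition, not a continuing check.
- *Two events in each part would show that the dose exceeds 7%.* 4/36 is 11.1%, but the exact 95% interval is 3.1% to 26.1%, which includes 7%.
- *Separate evaluation is itself a flaw.* FDA requested it because risk may differ by prior therapy, and Section 3.1.2 judges the optimal dose within each population.

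The extent of overlap at 40 x 10^6 is also unknown. Part II treats 6 patients at 20 x 10^6 first, with at least 3 reaching Week 12 before the next level opens.

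**Conclusion.** The point holds as an inconsistency with a missing link. Section 11.1, Section 11.2 and the parallel-start argument in Section 11.3 do not agree on the tolerable cardiac count. Followed as written, a Part I breach at 40 x 10^6 leaves Part II accrual at that dose unchanged.

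Between true rates of 3% and 15%, discordant final counts have a probability of 4.7% to 19.2% on a 24-patient denominator and 4.6% to 14.0% on a 30-patient denominator, in both cases highest at 10% among the rates tabulated. This rests on independent parts and an equal true rate. The second assumption is open to doubt, because the plan itself says the populations may differ.

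The documents do not show that Part II did or would continue on an unsafe dose, and they do not settle which limit was intended. The finding warrants an amendment but does not invalidate the design.

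**What to change.** Reconcile Sections 3.1.2, 11.1, 11.2 and 11.3 so that they state:

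1. which cardiac limit governs Part II, at which dose and over which denominator;
2. whether the tolerance of 0 to 2 of the next 10 in Section 11.3 or the 2-of-12 limit in Section 11.1 applies to the Part I expansion;
3. what a finding in one part that 40 x 10^6 is above a safe level means for accrual at that dose in the other part, and who acts on it. The action is for the sponsor and FDA to choose.

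As a descriptive supplement only, report the cardiac fraction at 40 x 10^6 over both parts (12 + 24 = up to 36 patients) beside the per-part results, with the 80% and 95% intervals already planned. Section 11.3 now lists denominators of 18, 24 or 30.

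The cost is amendment wording and one extra table, with no additional patients. The small downside is that the combined fraction mixes populations whose risk may differ, so it should not replace the per-part estimates.

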#### 1.2.4 Central and Peripheral Tolerance in the Transgenic HER2 Mouse Model

It should be noted that HER2/neu-transgenic mice have central or thymic tolerance to the oncogene, which is expressed from before birth (unlike some models in which an oncogene is not expressed until sexual maturity). They express a smaller, more limited and different T cell repertoire from that in non-transgenic mice, reflecting the deletion of many T cell clones by central self-tolerance. Thus, it is not surprising that it has been harder to treat established spontaneous tumors in the *neu*-transgenic mice. Further, in the BALB-*neu* transgenic model, the oncogene is expressed in all mammary cells of all mammary glands. As a consequence, relentless malignant transformation of mammary gland cells is induced with subsequent generation of independent primary tumors in all 10 mouse mammary glands, making it extremely difficult to suppress all tumors. In contrast, it is still possible to virtually completely suppress the development of tumors in *neu*-transgenic mice if vaccination is started at a young age, about 7 weeks, when histopathology already shows development of abnormal mammary gland dysplasia (beginning even before 4 weeks) due to the oncogene. Presumably the vaccine-induced antibodies are eradicating or inhibiting the dysplastic *neu*-expressing cells. Thus, this is really a therapeutic model, not just prophylactic. This situation contrasts with the human breast cancer situation, in which the HER2/*neu* oncogene is not expressed until malignant transformation in adulthood, so there is no opportunity to develop central tolerance. Indeed, Disis and coworkers have demonstrated that many patients with HER2+ breast cancers

express spontaneous antibodies and T cell responses to the HER2 oncoprotein, demonstrating the absence of central tolerance. Further, humans with breast cancer generally do not have such an oncogene expressed in 100% of mammary gland ductal epithelial cells as in the transgenic mice, leading to the relentless and continuous generation of new independent tumors. Therefore, it is expected that the vaccine will be more effective at inducing therapeutically effective antibodies to HER2 in patients with HER2+ breast cancers than it can in centrally tolerant neu-transgenic mice.

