If no DLTs are observed, then dose levels in Part I and Part II will be assessed for the fraction of patients with immunogenicity and clinical outcomes to determine the biologically optimal vaccine dose that would be used in any future phase II studies involving those respective patient populations.

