### **11.1 PART I (MAXIMUM OF 30 EVALUABLE PATIENTS)**

The goal of Part I is to investigate vaccine dose escalation and determine whether there is a significant, adverse safety signal regarding cardiac toxicity in patients with recurrent or progressive, metastatic solid tumors as well as adjuvant bladder cancer patients with HER2 expressing tumors that are naive to trastuzumab, lapatinib, ado-trastuzumab and other HER2-directed therapies, in addition to preliminary assessment of the vaccine's immunogenicity and clinical activity. Allowable tumors include breast, ovarian, colon, non-small cell lung, renal cell, bladder and prostate cancer with HER2 characterization by IHC and FISH as outlined in Section **2.1.1.14**.

Inclusion of a broad spectrum of tumors that express HER2 will facilitate more rapid accrual and allow prompt determination of the vaccine's safety and immunogenicity. However, the inclusion

of subjects with multiple tumor types that have varying levels of HER2 expression may preclude identification of an optimal biologically active dose.

During this part, vaccine safety, immunogenicity and preliminary activity will be determined for each dose level given escalating doses of vaccine as follows:

Dose Level 1 (N = 6 patients):	$5 \times 10^6$ viable cells/vaccine
Dose Level 2 (N = 6 patients):	$10 \times 10^6$ viable cells/vaccine
Dose Level 3 (N = 6 patients):	$20 \times 10^6$ viable cells/vaccine
Expansion Cohort (N= 12 patients):	$40 \times 10^6$ viable cells/vaccine

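### Immunogenicity is analysed only as a responder fraction in small dose groups; a supplementary baseline-adjusted model of log antibody on dose would use the same samples better

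*Combined protocol and SAP*

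**What the plan says.** Immunogenicity is a primary objective (Section 1.1.1 and the opening of Section 11). Its only planned analysis is in Section 11.3: "The fraction of subjects with immunogenicity, defined as a 3-fold increase in anti-HER2/neu antibody concentration (measured as mcg/mL) or a 4-fold increase" in dilution titre over baseline, which "will be reported, along with 80% and 95% confidence intervals, at the following time points" listed there: Weeks 4, 8, 12, 28, 48, 52, 76, 100 and 124.

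For Part I, Section 11.1 adds that "vaccine safety, immunogenicity and preliminary activity will be determined for each dose level". Section 3.1.2 says that, if no DLTs are observed, dose levels in both Parts will be "assessed for the fraction of patients with immunogenicity and clinical outcomes to determine the biologically optimal vaccine dose" for later phase II studies.

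Section 3.1 sets the groups. Part I has 6, 6, 6 and 12 patients at 5, 10, 20 and 40 x10^6 viable cells. Part II has 6 at 20 x10^6 and 24 at 40 x10^6. Appendix 6 schedules quantitative anti-HER2 testing at Weeks 0, 8, 16, 24, 32, 40, 48, 60, 76, 100 and 124, and the study calendar (Section 3.4) agrees.

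No model, contrast or comparison rule across doses is given. Every operating characteristic in Section 11 concerns cardiac toxicity.

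**The concern.** The plan commits to a dose recommendation that depends partly on immunogenicity by dose level, but gives no method for estimating how antibody changes with dose. What it offers is a separate proportion in each group, three of the four Part I groups having six patients. Cutting a measured fold rise at one threshold discards how far each patient rose, and separate proportions do not use the ordering of the doses.

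Baseline also matters. Section 1.2.4 reports that many patients with HER2-positive breast cancer already "express spontaneous antibodies and T cell responses to the HER2 oncoprotein". Fold rise uses baseline only as a divisor; if the rise depends on the starting level, the fraction does not adjust for it.

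At stake is how much the antibody data can contribute to the dose taken into the next trial. The sera needed for a better estimate are already being collected.

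**Working it through.** **1. The plan's own figures.** None exists for immunogenicity. The 30 per Part is illustrated only for cardiac toxicity: P(3 or more of 30) is 6.0% at a true rate of 3% and 84.9% at 15%, matching the stated 6% and 85%. These say nothing about antibody.

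**2. Precision of the planned fractions.** Exact (Clopper-Pearson) limits for k of n are the α/2 quantile of Beta(k, n−k+1) and the 1−α/2 quantile of Beta(k+1, n−k).

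| Responders | 80% CI | 95% CI |
|---|---|---|
| 3/6 | 20% to 80% | 12% to 88% |
| 6/12 | 29% to 71% | 21% to 79% |
| 12/24 | 35% to 65% | 29% to 71% |

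If two doses had true responder rates of 20% and 60%, Fisher's exact test (two-sided 5%) would have power of 8% for 6 v 6, 27% for 6 v 12 and 29% for 6 v 24.

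**3. Trend in Part I under a graded response.** The documents give no SD, effect size or response shape, so these are assumptions: mean log2 rise of 0.5 at 5 x10^6, plus 0.4 per dose doubling, with normal errors. The geometric mean rise then goes from 2^0.5 = 1.4-fold to 2^1.7 = 3.2-fold.

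- Code the doses 0, 1, 2, 3 for 6, 6, 6, 12 patients. The mean is (6 + 12 + 36)/30 = 1.8, and Sxx = (6 + 24 + 108) − 30 × 1.8² = 40.8.
- The slope test has noncentrality 0.4 × √40.8 / SD = 2.555/SD on 28 df, one-sided 5%.
- The comparator is a Cochran-Armitage trend test on responders (log2 rise of at least log2 3 = 1.585), by simulation (20,000 trials).
- At SD 1.0 the true responder rates are Φ(0.5 − 1.585), Φ(0.9 − 1.585), Φ(1.3 − 1.585) and Φ(1.7 − 1.585), that is 14%, 25%, 39% and 55%.

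| SD (log2) | Noncentrality | Continuous, exact | Continuous, simulated | Responder trend, simulated |
|---|---|---|---|---|
| 1.0 | 2.55 | 80% | 81% | 61% |
| 1.5 | 1.70 | 51% | 50% | 38% |
| 2.0 | 1.28 | 35% | 35% | 27% |

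This comparison has no baseline covariate.

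**4. Sensitivity.** A second simulation (4,000 trials, two-sided 5%) assumed a correlation of −0.4 between baseline and change. For a rise going from 2-fold to 4-fold with SD 0.4 log10, Part I power was 39% with baseline adjustment, 34% without, and 21% for the exact responder trend test (25% asymptotic). At SD 0.7 it was 15% v 9% (adjusted v exact). In Part II (6 v 24), the same 2-fold and 4-fold means at SD 0.4 gave 41% v 18% (27% asymptotic).

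**5. If dose changes only who responds.** With responder rates rising from 20% to 80% and responders averaging 10-fold (SD 0.25 log10), Part I power was 69% (log model) v 74% (responder trend). With 10% to 60% it was 53% v 53%. With 20% to 80% and responders averaging 5-fold (SD 0.2) it was 66% v 59%.

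**6. Visits.** Of the weeks named in Section 11.3, Weeks 4, 12, 28 and 52 are absent from Appendix 6; Weeks 8, 48, 76, 100 and 124 match. Section 5.1 implies a Week 52 draw only when a confirmatory scan falls then. The calendar footnotes add that samples from Week 40 onwards are taken only from patients who have not progressed.

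**The case against.** The plan is modest about its aim. The opening of Section 11 seeks only an approximate estimate of immunogenicity, and intervals at two levels would make the imprecision visible. Sections 3.1 and 11.1 themselves concede that the mix of tumour types and HER2 levels may prevent an optimal dose from being found. All of this stands, and it is why the model belongs beside the fraction and not in its place.

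Three stronger readings are tempting and are not supported:

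- A reader might infer that the optimal dose rests on the responder fraction alone, so that noise from dichotomising decides it. Section 3.1.2 also names clinical outcomes, applies only if no DLTs are observed, and sets no rule of picking the highest fraction.
- A reader might infer that the plan ignores baseline. The endpoint is already a rise over baseline; what is missing is covariate adjustment. The statement on pre-existing antibody concerns HER2-positive breast cancer, whereas Part I enrols many tumour types.
- A reader might infer that the model would detect a dose effect far more often. The gain depends on a response shape and SD that the documents do not give, and it vanishes or reverses in some all-or-none settings.

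The model has limits too. Dose is assigned by enrolment order, and adjuvant bladder patients enter Part I only after 12-week safety in at least 10 patients, so case mix can shift with dose. Part II has two doses and supports a difference, not a trend.

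**Conclusion.** The point holds as an analysis gap. A primary endpoint measured on a quantitative scale is reduced to a fraction in groups as small as six, that fraction feeds a dose decision, and no estimate across doses is planned. The imprecision follows directly from the group sizes. The benefit of the alternative is conditional: about 8 to 20 percentage points of power in Part I under the assumed graded response, and little or none if dose changes only who responds. Even with the model, power is about 50% or lower in two of the three graded settings in step 3. The analysis would therefore improve the description of dose and antibody; it would not by itself establish an optimal dose.

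**What to change.** Keep the responder fraction as planned and add a supplementary analysis to Section 11.3, separately by Part:

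- Outcome: log anti-HER2 concentration at one pre-specified visit, with log baseline (Week 0) as covariate.
- Part I: regress on log2 dose and report the slope per dose doubling.
- Part II: report the difference between 20 and 40 x10^6.
- Both Parts: give the geometric mean fold rise for each dose level. Report all estimates with 80% and 95% CIs.
- State in advance how values below the assay limit are handled.
- First reconcile the weeks in Section 11.3 with Appendix 6 and the calendar, then choose a visit that is actually sampled. A visit before Week 40 avoids restricting the analysis to patients who have not progressed.
- State that the slope and the difference are descriptive, because dose is confounded with enrolment order and tumour mix.

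The cost is SAP wording and a small amount of analysis, with no new patients, visits or samples.
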